Pediatric primary care systems are uniquely positioned to reduce HIV and STI incidence in adolescents, despite substantial challenges to sexual health service delivery. Health coaching is a developmentally appropriate and effective method of targeting motivation and behavior change in adolescents.

Objectives: (primary and important secondary objectives)

Primary Aim 1: To adapt a health coaching intervention to provide comprehensive, PrEP-inclusive, HIV and STI prevention for adolescents at elevated risk of HIV in pediatric primary care

Primary Aim 2: To identify contextual barriers and facilitators to implementation of the adapted health coaching intervention in pediatric primary care

Primary Aim 3: To conduct a randomized controlled trial (RCT) to test for the intervention's effect on HIV prevention self-efficacy, as well as feasibility and acceptability among adolescents at high risk of STI and HIV acquisition

Study Design:

Aim 1: Observational cross-sectional study

Aim 2: Observational cross-sectional study

Aim 3: Randomized control trial

Setting/Participants:

All aims: Participants will be recruited in-person or via telephone or email from CHOP Primary Care Clinics. Research activities will also be conducted at the Roberts Center for Pediatric Research, as well as primary care clinics, and on a virtual platform capable of video conferencing using a HIPAA compliant CHOP approved vendor.

In addition, for Aim 1, participants will also be recruited from the Adolescent Specialty Clinic (ASC) at [name]. In addition, participants can be referred by word-of-mouth from other study participants.

Key eligibility criteria

Aim 1: n= 50 male and female participants ages 13-19, with a history of one or more STIs, and can speak and understand written English, and has access to internet, a mobile device or computer, and video conferencing using a HIPAA compliant CHOP approved vendor.

Aim 2: n= 25 clinicians, clinic staff, and administrators who have provided clinical care to patients with STI diagnosis in the past 6 months and can speak and understand written English.

Aim 3: n=150 participants, 75 for each arm (with the chance of more participants in the RCT's intervention arm than control arm if there are changes to the randomization scheme). HIV-negative youth ages 13-19 within 30 days of treatment for an STI diagnosis of incident gonorrhea, chlamydia, trichomonas, or syphilis at the aforementioned clinics, and can speak and understand written English.

Study Interventions and Measures:

Aim 1: Observational study identifying barriers and facilitators to HIV/STI prevention strategies through surveys, virtual or in-person in-depth interviews and focus groups.

Aim 2: Observational study identifying acceptability, feasibility, and appropriateness of the coaching intervention through survey individual semi-structured interviews and chart-simulated recall.

Aim 3: Randomized controlled trial of the health coaching intervention designed to increase perceived self-efficacy in STI and HIV prevention, using survey measures, interviews, and chart abstraction for outcome measurement.

TABLE 1: SCHEDULE OF STUDY PROCEDURES FOR AIM 3 RCT

Study procedures, by treatment group for the Aim 3 randomized controlled trial.											
	Screening and Enrollment	Baseline		1 Week + 7/- 5 days		1 Month + 30/- 14 days		3 Months + 30/- 14 days		6 Months +/- 30 days	
Study procedure		HC ¹	SOC ²	HC	SOC	HC	SOC	HC	SOC	HC	SOC
Review of Inclusion / Exclusion Criteria	X	--	--	--	--	--	--	--	--	--	--
Informed Consent	X	--	--	--	--	--	--	--	--	--	--
Randomization	--	X	X	--	--	--	--	--	--	--	--
CASI ³	--	X	X	X	--	--	--	X	X	X	X
Health Coaching	--	X	--	X	--	X	--	X	--	--	--
Feedback Interview	--	--	--	--	--	--	--	X	--	--	--
Chart Abstraction	--	X	X	--	--	--	--	X	X	X	X

¹HC: Health coaching arm

²SOC: Standard of care arm

³Computer assisted survey instruments

1 BACKGROUND INFORMATION AND RATIONALE

1.1 Introduction

The proposed research seeks to: 1) adapt an existing Health Coaching intervention to focus on comprehensive adolescent biobehavioral HIV/STI prevention; 2) identify barriers and facilitators to intervention implementation in pediatric primary care; and 3) test the intervention in two high STI-incidence pediatric primary care clinics. If successful in accomplishing my aims, I will generate an intervention and dissemination strategy that are feasible to implement in primary care and poised to test whether it improves HIV prevention outcomes while simultaneously launching an independent career in HIV/STI prevention research.

1.2 Name and Description of Intervention

The third aim of this cluster of studies will consist of a randomized controlled trial of a health coaching intervention for adolescents with diagnosed sexually transmitted infections (STIs). The coaching sessions will provide HIV/STI prevention education and teach motivational interviewing (MI) and Acceptance and Commitment Therapy (ACT)-informed behavior change strategies using didactics, role plays, and patient encounter observations.

1.3 Relevant Literature and Data

Pre-exposure prophylaxis (PrEP) is the newest evidence-based practice for HIV prevention in adolescents. PrEP has arrived in the context of disproportionate rates of HIV infection and rising sexually transmitted infections (STIs) in adolescents. While 13-24 years olds comprise ~13% of the U.S. population, they represent 21% of incident HIV cases. STIs in the U.S. are rising dramatically,¹ with ~50% of incident STIs occurring in youth aged 15-24.² These statistics highlight the need for new strategies to reduce adolescent HIV and STI incidence. In adult clinical trials, oral tenofovir-emtricitabine (TDF-FTC)-based PrEP has been >90% effective in preventing HIV in highly adherent users.^{3,4} The Adolescent Trials Network (ATN) 110/113 trials recently demonstrated PrEP safety in adolescents, leading to expanded Food and Drug Administration (FDA) approval in 2018.^{5,6} The Centers for Disease Control and Prevention (CDC) now recommends PrEP for HIV negative individuals who are sexually active and not in a relationship with a recently tested HIV negative partner and have a recent STI, infrequent condom use with partners of unknown or high-risk HIV status, or are men who have sex with men (MSM) with recent condomless anal sex.⁷ As prevention options expand, there is a critical need for behavioral HIV prevention interventions to keep pace to ensure that PrEP reaches youth at highest risk of HIV infection.

CDC guidelines situate PrEP within comprehensive HIV/STI prevention care.⁷ Patients must be monitored every three months for risk reduction counseling, HIV, and STI testing. Given the dramatic recent rise in adolescent STIs and potential STI increases in PrEP users, PrEP must also be paired with STI prevention approaches.⁸ Unfortunately, while PrEP is known to be effective and safe for adolescents, <2% of PrEP prescriptions are for adolescents <18 years. To move PrEP to scale, research is needed to determine **who** should be involved in PrEP delivery, **what** the behavioral targets are for risk reduction, **which**

factors may serve as barriers to uptake, **when** the optimal time is for linkage to PrEP, and **how** to best intervene to increase HIV and STI prevention behavior in adolescents.

Pediatric primary care systems are uniquely positioned to reduce HIV and STI incidence in adolescents, despite substantial challenges to sexual health service delivery. While most youth will be in the care of a pediatrician when their STI or HIV infection occurs, currently, there is no evidence-based comprehensive biobehavioral HIV prevention framework for integrating PrEP in pediatric primary care. The U.S. Preventative Services Task Force (USPSTF), CDC, and American Academy of Pediatrics (AAP) all recommend routine HIV/STI screening and counseling at primary care visits, and the USPSTF recently gave PrEP a Grade A recommendation for individuals at high risk of HIV infection.⁹⁻¹³ However, there are significant discrepancies between guidelines and current practice. A survey of U.S. pediatric primary care providers (PCPs) found that <50% recommended routine STI and HIV testing to their adolescent patients.¹⁴ The most common barriers to sexual health delivery are lack of time and provider self-efficacy.¹⁵ Addressing all currently recommended prevention topics AND delivering PrEP to high-risk youth would require a substantial increase in the time currently allotted for pediatric visits. Since ‘buying’ providers additional time to provide comprehensive prevention is infeasible, this research will adapt a theory-driven health coaching intervention to increase HIV/STI prevention behavior in adolescents, paired with clinician delivery of PrEP.

Health coaching is a developmentally appropriate and effective method of targeting motivation and behavior change in adolescents. Coaches utilize motivational interviewing (MI) to facilitate behavior change, and strategies grounded in Acceptance and Commitment Therapy (ACT),¹⁶ a mindfulness-informed cognitive behavioral therapy, to educate, create prevention social norms, and nurture self-efficacy to adopt and sustain target behaviors. Coaches are typically allied health professionals who complete manualized and certified training.¹⁷ Coaching interventions are generally intensive programs that involve weekly-monthly 30-60 minute sessions over 1-6 months. Although time-intensive, a USPSTF systematic review found that only high-intensity risk reduction interventions (>2 hours total) significantly reduce STIs in adolescents.^{18,19} While PCPs are essential for PrEP delivery, the counseling time needed to create effective behavior change is infeasible in the routine office setting. Instead, this counseling can be delivered by coaches who can meet repeatedly with patients to develop and enact tailored risk reduction plans and then partner with PCPs who can prescribe PrEP. Cost-benefit analyses demonstrate that health coaching can lead to significant savings in expenditures for >20 chronic health conditions, making it a promising option for high-value care delivery.²⁰

To create an effective AND scalable intervention, we aim to develop and test an intervention that has the capacity to be implemented in pediatric primary care. Most HIV and STI prevention interventions have focused on key sub-populations of adolescents such as young men and transgender women who have sex with men (YMSM/TW) who comprise the vast majority of incident HIV infections, or young women who carry the disproportionate burden of morbidity associated with STIs but are overlooked in PrEP interventions.²¹⁻²³ However, in primary care, there is a need for interventions such as health coaching which can be broadly applied to adolescents, but tailored to the needs of specific

demographic populations. Lastly, while coaches may be essential in moving youth toward PrEP uptake, PCPs will be necessary for prescription and medical management. Unfortunately, even among Adolescent Medicine specialized pediatricians, only 35% have prescribed PrEP and the odds of prescription are double in those who feel confident in their PrEP knowledge.²⁴ Therefore, for this research, we will involve multi-level stakeholders in implementation research addressing the integration of coaching and, in tandem, PrEP delivery in primary care.

1.4 Compliance Statement

This study will be conducted in full accordance all applicable Children's Hospital of Philadelphia Research Policies and Procedures and all applicable Federal and state laws and regulations including 45 CFR 46. All episodes of noncompliance will be documented.

The investigators will perform the study in accordance with this protocol, will obtain consent and assent, and will report unanticipated problems involving risks to subjects or others in accordance with The Children's Hospital of Philadelphia IRB Policies and Procedures and all federal requirements. Collection, recording, and reporting of data will be accurate and will ensure the privacy, health, and welfare of research subjects during and after the study.

2 STUDY OBJECTIVES

The overarching purpose of this study is to optimize HIV and STI prevention delivery in primary care by adapting, optimizing, and testing a youth-focused, health coaching intervention to deliver comprehensive HIV/STI prevention, including PrEP, to high-risk adolescents.

2.1 Primary Objective (or Aim)

There are three primary aims to this study:

Primary Aim 1: To adapt a health coaching intervention to provide comprehensive, PrEP-inclusive, HIV and STI prevention for adolescents at elevated risk of HIV in pediatric primary care

Primary Aim 2: To identify contextual barriers and facilitators to implementation of the adapted health coaching intervention in pediatric primary care

Primary Aim 3: To conduct a randomized controlled trial (RCT) to test for the intervention's effect on HIV prevention self-efficacy, as well as feasibility and acceptability among adolescents at high risk of STI and HIV acquisition.

3 INVESTIGATIONAL PLAN

3.1 General Schema of Study Design

The project will be conducted as part of a K23 career development award with three aims. Each aim represents a sub-study of the overarching study to achieve the overall goal. Aims 1 and 2 will occur sequentially and each should take approximately a year to complete. The results of Aim 1 and 2 will go to inform the randomized control trial (RCT) in Aim 3. However, Aim 3 enrollment can occur even if there is no enrollment in Aim 2. Aim 3 will occur over a 12-18-month period.

Aim 1: Observational, qualitative, cross-sectional study (n~50). Youth with complete one of five focus groups (~5-8 youth per group) or an in-depth interview to identify barriers and facilitators to HIV/STI prevention behavior to be addressed in the intervention and determine preferences for intervention format and delivery strategy. Participants will also complete a brief CASI at the time of study enrollment after informed consent. At the end of each focus group and in-depth interview, we will remind participants of where they can access sexual health and preventative care services and we will share the clinics' contact information. It is of note that Aim 1 focus groups might not occur if any conditions prohibit the gathering of focus groups within the primary care setting.

Aim 2: Observational, mixed methods using chart stimulated recall (CSR), in-depth interviews, and quantitative measurement of acceptability, feasibility and appropriateness of the PrEP-inclusive coaching intervention in pediatric primary care. Participants will complete a single study visit with completion of CSR, semi-structured audio-recorded interviews, and a computer assisted survey instrument (CASI) delivered on a secure tablet or laptop with acceptability, feasibility, and appropriateness measures.

Aim 3: We will conduct 1) an iterative pilot phase followed by 2) a small RCT assessing intervention effect on the intermediate target of prevention self-efficacy. Pilot testing will occur over a 3-month period to prime intervention for implementation, with the aim of recruiting n=10 pilot participants. Pilot phase participants will follow the same study procedure timeline as participants randomized to the coaching intervention arm of the RCT, excluding the 6-month follow-up visit. Pilot participants will not be followed in the RCT or contribute outcome data. At the end of every health coaching visit (the baseline, 1-week, 1-month and 3-month visits), pilot phase participants will complete a brief feedback interview to ensure face validity and identify areas needing refinement. Feedback will be incorporated into the study design, with amendments submitted to the IRB as needed. The RCT will randomize youth with recent STI 1:1 to the coaching intervention vs a standard of care (SOC) control. If difficulty retaining coaching participants during the RCT generates a disparity in evaluable participants per arm, the RCT's randomization scheme will be changed to 2:1, intervention vs SOC, to balance numbers of evaluable participants per arm. Both arms (intervention and SOC) will have data collection visits at the baseline, the 3-month, and the 6-month-follow-up time points. In addition, the intervention group will have health coaching sessions at baseline, 1 week, 1 month and 3 months. At the end of the 3-month health coaching visit, a sample of RCT phase participants assigned to the intervention arm will complete a brief feedback interview to ensure face validity and identify areas needing refinement for future studies.

3.1.1 Screening Phase

Aim 1: Participants for the virtual or in-person in-depth interviews and focus groups will be identified through the CHOP STI testing database, a data platform with >20,000 HIV/STI testing encounters (2014-present) which updates in near-real time using a business intelligence application (Qlik, Radnor, PA). The password-protected dataset application is only accessible to the principal investigator (PI) and the study team. Potential subjects will be identified using the protocol inclusion and exclusion criteria. Study staff be provided a list of potential participants via the Pediatrics Research Consortium (PeRC) and will confirm participant eligibility criteria in the electronic health record (EHR), based on age and prior STI status. Participants can also be recruited in-person by the research team from the CHOP Adolescent Specialty Clinic and referred into the study by word-of-mouth from existing study participants. For all participants, consent for the study will occur via a Research Electronic Data Capture (REDCap) form and can occur in-person or via a secure online form emailed from the REDCap platform. Participants will not be told on the consent form that they are being recruited because they are diagnosed with an STI. This is because knowing this information would inform the participants of the health information of the others in the focus group. Given the sensitive nature of the data and enrollment of minor adolescents, per the guidance of the CHOP REDCap team, participant's personal email addresses will be collected via the consent form to mitigate the use of any potential auto-default parent/guardian email addresses via MyCHOP, and to ensure participants receive a copy of their signed/e-signed consent form.

Aim 2: Clinical provider participants will be identified through assistance by PeRC. We will solicit a list of names and emails of those who are in the clinical practices meeting the inclusion criteria at CHOP Karabots and Cobbs Creek clinics. All potential participants will be sent an email through the secure CHOP system asking if they are interested in participating in a research study and detailing brief study information. From an email survey link, potential participants can access the secure REDCap screening survey to determine eligibility.

Aim 3: Potential clinical trial participants will be identified and referred for recruitment by any of three strategies: 1) when nurses or clinical providers call with positive STI results, they will provide adolescent patients with information about the study; 2) the STI database will be checked daily by the study team to identify new STI diagnoses and obtain the confidential contact information for potential participants to contact them directly by phone; and 3) potential participants will be approached in-person at the time of STI testing or treatment. Screening for the study will occur via a REDCap form and can occur in person or by phone.

3.1.2 Study Treatment Phase

Aim 1: No intervention

Aim 2: No intervention

Aim 3: The study treatment phase for the RCT will consist of data collection and health coaching visits over a 6-month period (see Table 1: Schedule of Study Procedures for Aim 3

RCT). The health coaching sessions will consist of HIV and STI prevention education, motivational interviewing, and acceptance and commitment therapy.

3.1.3 Follow-up Phase

Aim 1: No intervention

Aim 2: No intervention

Aim 3: All RCT participants will have a 6-month follow-up visit. Participants in the intervention arm will be able to attend the follow-up visit if they attend at least one of the health coaching visits. For both arms, the follow up visit will consist of the same data collection (CASI and chart abstraction) as the 3-month visit.

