4.2 Study Intervention Phase

Aim 1: No intervention

Aim 2: No intervention

Aim 3: The discussion of the intervention phase is strictly for Aim 3 of the study project.

For the Aim 3 RCT phase, the participants randomized to the standard of care group will not undergo the health coaching intervention. The participants randomized to the health coaching group will attend health coaching sessions at the baseline, 1-week, 1-month and 3-month visits.

4.2.1 Follow up Visit 1

Aim 1: N/A

Aim 2: N/A

Aim 3: Both the health coaching group and the standard of care group will complete follow-up surveys at the 6-month follow-up visit.

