4.4 Subject Completion/Withdrawal

Aims 1, 2, 3: Participant completion of the study will be closely monitored in both treatment arms. Our criteria for defining study completion, withdrawal, drop out, and attrition is defined below.

Multiple attempts will be made to retain participants in the study. Participants in either treatment group who do not attend a visit after 3 unsuccessful contact attempts will be considered a no-show for that visit.

Subjects may withdraw from the study at any time without prejudice to their care. They may also be discontinued from the study at the discretion of the Investigator for lack of adherence to visit schedules. The Investigator may also withdraw subjects who violate the study plan, or to protect the subject for reasons of safety or for administrative reasons. It will be documented whether or not each subject completes the study. If the Investigator becomes aware of any serious, related adverse events after the subject completes or withdraws from the study, they will be recorded on the CRF.

Participants will be asked to provide at least three forms of secure contact information (e.g., cell phone, email, social media). In addition, participants will be asked about preferred method of contact, and will be asked for consent to text message. At the end of each study visit, participants will be scheduled for their next visit. We will use flexible visit windows for each coaching visit. Before the window opens, participants will be contacted via their preferred method to confirm their next appointment. If a participant does not respond after 2-3 attempts using one strategy (i.e., texting, emailing, calling) then a new outreach strategy will be used to diversify the approach. If a participant does not respond after five unanswered attempts, we will stop trying. Study staff will provide reminder contact (text, call or email) prior to each visit based on the participants preferred method. To facilitate follow up, the coaching sessions will not be restricted to the clinic, and instead coaches will

be able to meet youth in the community or over a CHOP-approved HIPAA compliant platform.

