6.3.2 Analysis

Aim 1: We will conduct a deductive qualitative analysis of focus group transcripts and in-depth interview transcripts with our theoretical model guiding the coding process. Codes related to model constructs will be assigned to interview segments to organize the data, using the software NVivo, with two study team members separately reviewing the first 10 transcripts line by line, assigning codes as concepts become apparent. We will compare text segments to those that have been previously assigned the same code, and to segments coded separately by each analyst, to decide whether they reflect the same concept. We will use this process to generate a coding scheme, then apply it to all transcripts. Once coding is complete, we will review the data to document emerging themes-general insights gleaned from the entirety of the data- which may inform intervention content.

Aim 2: Survey data will be summarized via descriptive statistics. We will set a >80% threshold for high acceptability, feasibility and appropriateness. The interview coding process will parallel that described in Aim 1. We will use an integrated deductive and inductive coding approach. Transcripts will be reviewed using deductive methodology, where CFIR determinants will be used as the coding framework. After completion, the transcripts will be re-reviewed using inductive methodology where codes identifying novel barriers and facilitators of implementation that do not map onto the CFIR will be identified and used to develop a coding framework that is then applied to all transcripts. We will integrate the qualitative and quantitative data by merging findings through a comparative coding analysis. The AIM and FIM scores will be dichotomized (completely disagree/disagree vs completely agree/agree). We will compare the distribution of content themes between providers with high vs low acceptability and, separately, high vs low feasibility ratings. Data will then be used as a starting point in which to build an optimized PrEP-inclusive coaching implementation strategy to be tested in the subsequent RCT.

Aim 3: The primary analysis will be based on an intention to treat approach and will include all subjects randomized at Visit 1.

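### Section 3.1.3 makes the coaching arm's six-month visit depend on attending a coaching session, against every other description of that visit

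*Combined protocol and SAP*

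**What the plan says.** All references are to Aim 3 of the combined protocol and SAP.

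- Section 3.1.3, first sentence: "All RCT participants will have a 6-month follow-up visit". The sentence after it: "Participants in the intervention arm will be able to attend the follow-up visit if they attend at least one of the health coaching visits".
- Section 3.1: "Both arms (intervention and SOC) will have data collection visits at the baseline, the 3-month, and the 6-month-follow-up time points".
- Section 4.2.1: "Both the health coaching group and the standard of care group will complete follow-up surveys at the 6-month follow-up visit".
- Table 1 marks the survey and chart abstraction at six months for both arms. Its footnotes only expand abbreviations.
- Section 7.1 has control participants complete the three- and six-month research visits without condition.
- Section 5.2 defines the primary outcome as the between-arm difference in change in self-efficacy from baseline to six months.
- Section 6.3.2: "The primary analysis will be based on an intention to treat approach and will include all subjects randomized at Visit 1". The model has a random intercept and a random slope for time.
- Section 4.4, on withdrawal: "They may also be discontinued from the study at the discretion of the Investigator for lack of adherence to visit schedules". On contact: "If a participant does not respond after five unanswered attempts, we will stop trying".
- Section 3.1 allows a change to 2:1 allocation: "If difficulty retaining coaching participants during the RCT generates a disparity in evaluable participants per arm".

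**The concern.** Two consecutive sentences of section 3.1.3 disagree about who has the visit at which the primary outcome is measured. If the second is applied, coaching participants with no session are not measured at six months, while control participants face no comparable hurdle. Collection of the primary outcome then depends on behaviour after randomisation, in one arm. That sits badly with an intention-to-treat comparison, although those participants remain in the model through their baseline score and any three-month score.

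The mixed model deals with the missing scores only if they are missing at random given the observed scores. Whether that holds for youth who attended no coaching is unknown. If they improve less than attenders, the estimate favours coaching. If they skip coaching because they are already confident, the error could go the other way.

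Two further points are secondary. The trigger for 2:1 allocation refers to evaluable participants without defining them; if that means having a six-month score, this condition adds to the disparity that sets off the switch. And section 4.4 does not say whether missed coaching alone counts as poor adherence to the visit schedule.

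**Working it through.** **1. The text.**

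| Place | Coaching arm at six months | Control arm at six months |
|---|---|---|
| 3.1.3, first sentence | all | all |
| 3.1.3, second sentence | if at least one coaching visit attended | no condition |
| 3.1 | all | all |
| 4.2.1 | all | all |
| Table 1 | survey and chart abstraction | survey and chart abstraction |
| 7.1 | not addressed | all |

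Nothing elsewhere withdraws the condition or says how a coaching participant with no session is followed. No condition is written for the three-month survey.

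**2. Can anyone be affected?** Yes. Section 9.1.1 places randomisation after the baseline survey, and coaching follows allocation, so a participant can be randomised and receive no session. Section 9.7 also treats a completed baseline session as something that distinguishes some coaching participants from others.

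**3. The plan's own yardstick.** Section 6.4 gives 75 per arm, 80% power, two-sided alpha 0.05, intra-subject correlation 0.01-0.3, up to 10% loss, and a detectable difference of 0.7-0.9 SD. A two-sample normal approximation gives (1.960 + 0.842) × √(2/75) = 0.46 SD of the change. Multiplying by √(2(1 − ρ)) gives single-visit SD units: 0.64 at ρ = 0.01 and 0.54 at ρ = 0.3. With 67.5 per arm after 10% loss these become 0.68 and 0.57. The low end of the stated range is nearly met and the high end is not reproduced. That is a separate matter; 0.7-0.9 SD serves here only as a scale.

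**4. Size of the shift (assumed inputs).** Let f be the share of the coaching arm with no session and d their shortfall against attenders. Neither is in the documents. I assume f = 5-20% (about 4-15 of 75) and d = 0.3-0.5 SD.

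- If all of them would otherwise have attended and only observed changes are compared, the shift is f × d: 0.05 × 0.3 = 0.015 SD to 0.20 × 0.5 = 0.10 SD. That is 0.015/0.9 = 1.7% to 0.10/0.7 = 14.3% of the stated difference.
- At f = 5% alone it is 0.015-0.025 SD, at most 0.025/0.7 = 3.6%.
- If only a share s would have attended, the shift is f·s·d / (1 − f(1 − s)). With s = 0.5 (assumed): 0.0075/0.975 = 0.008 SD to 0.05/0.90 = 0.056 SD.

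**5. What a mixed model leaves.** Section 6.3.2 calls the model logistic, but the score is continuous, so I take the linear form. Assume s = 1, equal baselines, three-month scores observed, and a three-month shortfall also equal to d.

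- Visit as a category, exchangeable correlation: f·d/(1 + ρ). The factor is 1/1.01 = 0.990 to 1/1.3 = 0.769, giving 0.0115-0.0990 SD.
- Linear time coded 0, 0.5, 1; intercept and slope variances both ρ, residual 1 − ρ; expected generalised least squares. At ρ = 0.01 the factor is 0.968 (f = 5%) and 0.904 (f = 20%); at ρ = 0.3 it is 0.613 and 0.536. This gives 0.0092-0.0904 SD.
- Slope variance four times larger: 0.22-0.95.
- Linear time with one common baseline mean for both arms: 0.46-0.78.

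So under these inputs the model reduces the shift but does not remove it.

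**6. Loss allowance.** 10% of 150 is 15 participants. Between 4 and 15 uncollected outcomes would use at most 4/15 = 27% to 15/15 = 100% of it.

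**The case against.** The strongest reply is that the sentence is permissive. It says such participants will be able to attend if they came to one session, not only if they did. Following directly on a sentence that gives everyone the visit, it may mean simply that missing some sessions does not cost a participant the follow-up. That reading contradicts nothing else in the protocol, whereas the strict reading contradicts several places.

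This is a fair reading and may be what was intended. But a permission tied to attending at least one session ordinarily sets a floor, and site staff could apply it that way. Even on the lenient reading, the sentence leaves the zero-session participant unaddressed.

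Other points stand in part:

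- Few people are likely to be affected. The first session is scheduled at baseline, and the missed-visit payment in section 9.7 covers youth who completed it. The low end of the range is the more plausible one.
- Some zero-session youth would be lost anyway, since contact stops after five unanswered attempts. Losing them despite effort still differs from not collecting their data by rule.
- The intention-to-treat population is not breached; the issue is missing outcomes within it.
- Every input to the size is assumed except the correlation range, and the mixed-model factors move with the model chosen. The figures show order of magnitude only.
- The 2:1 point depends on what evaluable means, and the discretion in section 4.4 applies to both arms.

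**Conclusion.** The concern holds. Section 3.1.3 contradicts itself and sections 3.1, 4.2.1 and Table 1 on who has the six-month visit. Read in its ordinary sense, it leaves the primary outcome uncollected in one arm because of post-randomisation behaviour. This rests on the text and needs no assumed number.

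The size and direction of any bias are unknown and the effect is probably small. Under the assumed shares and shortfalls the ceiling is 0.015-0.10 SD, and 0.015-0.025 SD if only 5% attend nothing. It should be fixed because the condition bears on the primary outcome and removing it costs almost nothing, not because a large distortion has been shown.

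**What to change.** Delete the condition in section 3.1.3 and replace it with wording such as: *The 3- and 6-month surveys and chart abstraction are sought for every randomised participant in both arms, whatever their coaching attendance, unless the participant withdraws or is withdrawn from the study.*

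Reconcile section 4.4 with this, so that missed coaching alone does not end outcome collection. The limits on contact attempts can stay. It would also help to define evaluable where the 2:1 switch is described.

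The cost is a wording amendment plus, under the assumed range, at most 4 × $40 = $160 to 15 × $40 = $600 in six-month payments. Section 9.7 already offers that payment to both arms without a coaching condition, so some or all of it may not be new spending.
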